8.3 ADVERSE EVENTS AND SERIOUS ADVERSE EVENTS

8.3.1 DEFINITION OF ADVERSE EVENTS (AE)

Adverse event means any untoward medical occurrence associated with the use of an intervention in humans, whether or not considered intervention-related (21 CFR 312.32 (a)).

8.3.2 DEFINITION OF SERIOUS ADVERSE EVENTS (SAE)

An adverse event (AE) or suspected adverse reaction is considered “serious” if, in the view of either the investigator or sponsor, it results in any of the following outcomes: death, a life-threatening adverse event, inpatient hospitalization or prolongation of existing hospitalization, a persistent or significant incapacity or substantial disruption of the ability to conduct normal life functions, or a congenital anomaly/birth defect. Important medical events that may not result in death, be life-threatening, or require hospitalization may be considered serious when, based upon appropriate medical judgment, they may jeopardize the participant and may require medical or surgical intervention to prevent one of the outcomes listed in this definition. Examples of such medical events include allergic bronchospasm requiring intensive treatment in an emergency room or at home, blood dyscrasias or convulsions that do not result in inpatient hospitalization, or the development of drug dependency or drug abuse.

8.3.3 CLASSIFICATION OF AN ADVERSE EVENT

8.3.3.1 SEVERITY OF EVENT

All reported adverse events will be classified using the Common Terminology Criteria for Adverse Events (CTCAE) developed and maintained by CTEP at National Cancer Institute. The intensity or severity of the AE will be graded as follows:

- **Grade 1:** Mild AE
- **Grade 2:** Moderate AE
- **Grade 3:** Severe AE
- **Grade 4:** Life-threatening or disabling AE
- **Grade 5:** Death related to AE

8.3.3.2 RELATIONSHIP TO STUDY INTERVENTION

All adverse events (AE) must have their relationship to study intervention assessed by the clinician who examines and evaluates the participant based on temporal relationship and his/her clinical judgment. The degree of certainty about causality will be graded using the categories below. In a clinical trial, the study product must always be suspect.

- **Related** – The AE is known to occur with the study intervention, there is a reasonable possibility that the study intervention caused the AE, or there is a temporal relationship between the study intervention and event. Reasonable possibility means that there is evidence to suggest a causal relationship between the study intervention and the AE.

- **Not Related** – There is not a reasonable possibility that the administration of the study intervention caused the event, there is no temporal relationship between the study intervention and event onset, or an alternate etiology has been established.

8.3.3.3 EXPECTEDNESS

The Pis will be responsible for determining whether an adverse event (AE) is expected or unexpected. An AE will be considered unexpected if the nature, severity, or frequency of the event is not consistent with the risk information previously described for the study intervention.

Common adverse events of sirolimus that have been described in previous clinical trials (> 10% of patients) include:

- Blood and lymphatic disorders (anemia, leucopenia, thrombocytopenia)
- Dermatological disorders (acneiform rash, oral mucositis)
- Dyslipidemia (high cholesterol, high lipids)
- Hyperglycemia/glucose intolerance/new onset diabetes mellitus
- Hypertension
- Lymphocele
- Pneumonitis
- Renal disorders (proteinuria/increased creatinine/increased blood urea)
- Wound complications (healing problems)
- Infections (urinary tract infection, pneumonia)

In addition, patients with MSA have increased morbidity associated to the motor and autonomic dysfunction inherent to the disease, regardless of any study drug or intervention. Expected events that are expected to occur as part of the natural history of MSA are:

- Urinary tract infection
- Dizziness, lightheadedness or feeling about to faint
- Syncope due to orthostatic hypotension
- Shortness of breath upon standing
- Head or neck pain/discomfort upon standing
- Blurry vision or other vision changes upon standing
- Falls
- Aspiration pneumonia

8.3.4 TIME PERIOD AND FREQUENCY FOR EVENT ASSESSMENT AND FOLLOW-UP

The occurrence of an adverse event (AE) or serious adverse event (SAE) may come to the attention of study personnel during study visits and interviews of a study participant presenting for medical care, or upon review by a study monitor.

All Aes including local and systemic reactions not meeting the criteria for SAEs will be captured on the appropriate case report form (CRF). Information to be collected includes event description, time of onset, clinician's assessment of severity, relationship to study product (assessed only by those with the training and authority to make a diagnosis), and time of resolution/stabilization of the event. All Aes

occurring while on study must be documented appropriately regardless of relationship. All Aes will be followed to adequate resolution.

Any medical condition that is present at the time that the participant is screened will be considered as baseline and not reported as an AE. However, if the study participant's condition deteriorates at any time during the study, it will be recorded as an AE.

Changes in the severity of an AE will be documented to allow an assessment of the duration of the event at each level of severity to be performed. AEs characterized as intermittent require documentation of onset and duration of each episode.

The PI will record all reportable events with start dates occurring any time after informed consent is obtained until 7 (for non-serious AEs) or 30 days (for SAEs) after the last day of study participation. At each study visit, the investigator will inquire about the occurrence of AE/SAEs since the last visit. Events will be followed for outcome information until resolution or stabilization.

8.3.5 NON-SERIOUS ADVERSE EVENT REPORTING

Non-serious expected adverse events: non-serious expected adverse events that are reported to or observed by the investigator or a member of his research will be presented in tabular form and given to the IMM on a bi-annual basis or as requested.

Non-serious Aes that are expected or unexpected but do not increase the risk of the study drug will be reported in annual reports to the IRB.

8.3.6 SERIOUS ADVERSE EVENT REPORTING

The research study team member will immediately report to the PI any serious adverse event, whether or not considered study intervention related, including those listed in the protocol or investigator brochure and must include an assessment of whether there is a reasonable possibility that the study intervention caused the event.

Serious adverse events (e.g., death, hospitalizations) with evidence suggesting a probable or possible causal relationship between the study intervention and the event (e.g., death from anaphylaxis) will be reported by the PI or study coordinator to the IRB and the IMM **within 7 working days** after the PI's initial receipt of the information. If required, emergency unblinding will follow the criteria specified in section 6.3.

Serious adverse events (e.g., death, hospitalizations) with no evidence of a causal relationship between study intervention and event need to be communicated to the IMM **within 14 working days** after the PI's initial receipt of the information.

All serious adverse events (SAEs) will be followed until satisfactory resolution or until the site investigator deems the event to be chronic or the participant is stable. Other supporting documentation of the event may be requested by any regulatory agency and should be provided as soon as possible.

The PI will be responsible for notifying the IRB, IMM and Food and Drug Administration (FDA) of any unexpected fatal or life-threatening suspected adverse reaction as soon as possible, but in **no case later than 7 calendar days** after the PI's initial receipt of the information. Emergency unblinding will follow the criteria specified in section 6.3.

8.4 UNANTICIPATED PROBLEMS

8.4.1 DEFINITION OF UNANTICIPATED PROBLEMS (UP)

The Office for Human Research Protections (OHRP) considers unanticipated problems involving risks to participants or others to include, in general, any incident, experience, or outcome that meets **all** of the following criteria:

- Unexpected in terms of nature, severity, or frequency given (a) the research procedures that are described in the protocol-related documents, such as the Institutional Review Board (IRB)-approved research protocol and informed consent document; and (b) the characteristics of the participant population being studied;
- Related or possibly related to participation in the research ("possibly related" means there is a reasonable possibility that the incident, experience, or outcome may have been caused by the procedures involved in the research); and
- Suggests that the research places participants or others at a greater risk of harm (including physical, psychological, economic, or social harm) than was previously known or recognized.

8.4.2 UNANTICIPATED PROBLEM REPORTING

The investigator will report unanticipated problems (Ups) to the reviewing Institutional Review Board (IRB) and to the principal investigator (PI). The UP report will include the following information:

- Protocol identifying information: protocol title and number, PI's name, and the IRB project number;
- A detailed description of the event, incident, experience, or outcome;
- An explanation of the basis for determining that the event, incident, experience, or outcome represents an UP;
- A description of any changes to the protocol or other corrective actions that have been taken or are proposed in response to the UP.

To satisfy the requirement for prompt reporting, Ups will be reported using the following timeline:

- Ups that are serious adverse events (SAEs) will be reported to the IRB and to the IMM within **7 working days** of the investigator becoming aware of the event.
- Any other UP that significantly increases the risk of the study will be reported to the IRB and to the IMM within **7 working days** of the investigator becoming aware of the problem.
- All UP that do not increase the risk of the study will be reported to the IMM in the bi-annual safety report.

9 STATISTICAL CONSIDERATIONS

9.1 STATISTICAL HYPOTHESES

Primary Efficacy Endpoint: We hypothesize that treatment with sirolimus will show promise to slow the progression of the disease of patients with MSA. Specifically, our null hypothesis is that patients receiving sirolimus will have a UMSARS total score progression of only 4.6 points at week 48 higher than baseline, compared to a progression of 8.6 points at week 48 from baseline reported in historical controls from natural history studies and placebo-controlled trials of MSA. Our alternate hypothesis is that sirolimus will be futile to slow the progression of the disease in patients with MSA. The statistical definitions are as follows:

$H_0: \theta_E - \theta_p \leq 4$ where $\theta_p = 8.6$ points increase at week 48 from baseline described in historical controls
 $H_0: \theta_E \leq 4.6$ points increase at week 48 from baseline
 $H_1: \theta_E > 4.6$ points increase at week 48 from baseline

Secondary Efficacy Endpoints:

Brain MRI: We hypothesize that treatment with sirolimus will slow the increase of putaminal diffusivity in patients with MSA. Specifically, our null hypothesis states that patients receiving sirolimus will have a putaminal Trace (D) total score progression of 0.030×10^{-3} mm²/sec or less at week 48 versus baseline, compared to a progression of 0.070×10^{-3} mm²/sec at week 48 from baseline reported in specific longitudinal studies of MSA (41).

$H_0: \theta_E - \theta_p \leq 0.04$ where $\theta_p = 0.07$ ($\times 10^{-3}$ mm²/sec) increase in putaminal diffusivity at week 48 from baseline described in specific studies
 $H_0: \theta_E \leq 0.03$ points increase at week 48 from baseline
 $H_1: \theta_E > 0.03$ points increase at week 48 from baseline

Optical coherence tomography: We hypothesize that treatment with sirolimus will slow the thinning of the retinal nerve fiber layer (RNFL) in patients with MSA. Specifically, our null hypothesis states that patients receiving sirolimus will have a RNFL thickness thinning of 1.45 μ m at week 48 versus baseline, compared to a decrease of 3.7 μ m at week 48 from baseline reported in specific longitudinal studies of MSA (12).

$H_0: \theta_E - \theta_p \leq 2.25$ where $\theta_p = 3.7$ μ m decrease in RNFL at week 48 from baseline described in specific studies
 $H_0: \theta_E \leq 1.45$ μ m decrease at week 48 from baseline
 $H_1: \theta_E > 1.45$ μ m decrease at week 48 from baseline

Concentration of exosomal α Syn particles: We hypothesize that treatment with sirolimus will reduce the concentration of exosomal α Syn particles in patients with MSA. Specifically, our null hypothesis is that patients receiving sirolimus will have statistically lower concentration of exosomal α Syn particles at week 48 compared to baseline:

$H_0: \theta_E < \theta_p$
 $H_1: \theta_E \geq \theta_p$

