
To assess the potential effects of sirolimus on brain neuroimaging and retinal biomarkers in patients with MSA
	
Brain magnetic resonance changes using dedicated algorithms to evaluate rate of change in diffusivity of defined areas of brain from baseline to 48 weeks in patients receiving sirolimus compared to the progression of putaminal diffusivity reported in longitudinal studies of MSA.
	
Increased putaminal diffusivity has been consistently reported, even in early disease stages of MSA (42, 55-59). Increase in putaminal diffusivity has been reported to be a sensitive neuroimaging measures of disease progression in patients with MSA and has been used previously as neuroimaging

OBJECTIVES	ENDPOINTS	JUSTIFICATION FOR ENDPOINTS
	
Changes in retinal nerve fiber layer (RNFL) using optical coherence tomography from baseline to 48 weeks in patients receiving sirolimus compared to the rate of progression in longitudinal studies of MSA.
	
outcome measure in previous clinical trials of MSA (41, 42).
 
The use of optical coherence tomography (OCT) is emerging as a non-invasive fast technique to measure the thickness of the retinal layers. Even though patients with MSA only rarely have visual complaints, recent studies by our group using OCT showed that the retina of patients with MSA have consistent atrophy of the peripapillary retinal nerve fiber layer (RNFL) and to a lesser extent the macular ganglion cell layer (GCL) complex (13). These abnormalities are progressive overtime and have been recently confirmed by pathological examination in the retinas from three patients with MSA (12, 14).

Tertiary/Exploratory		

To explore the effects of sirolimus on blood biomarkers (exosomal alpha-synuclein particles) in patients with MSA
	
Change from baseline to week-48 in exosomal alpha-synuclein particle concentration in plasma in patients taking sirolimus versus the placebo group
	
The concentration of exosomal alpha-synuclein particles in plasma has been proposed as a biomarker of diagnosis of synucleinopathies. We hypothesize that sirolimus will increase autophagy and, therefore, the degradation of these exosomal alpha-synuclein particles.

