9.2 SAMPLE SIZE DETERMINATION

This study is a randomized, double blind placebo-controlled futility trial in which the primary outcome measure value (UMSARS total score) in a cohort of patients with MSA taking active agent will be compared to a known value from historical controls previously published in the literature. The primary outcome measure was used to calculate the sample size.

The primary statistical analysis will involve a comparison of the mean absolute difference in the active sirolimus group with a pre-specified fixed value, constituting a 4-point reduction in the expected mean increase in the UMSARS total score over 48 weeks without treatment. The expected mean increase in total UMSARS outcomes were obtained from the *U.S. Natural History Study of MSA* (n=96) (39), that reported that the total UMSARS score at 12 months increased a mean of 7.5 (SD: 8.4) absolute points from baseline. Also data from a phase III double-blind placebo-controlled 12-month clinical trial with rifampicin in MSA performed in the U.S. (40) (which was found to be ineffective to slow the progression of the disease) showed that in patients taking placebo (n=50) the total UMSARS score at 12 months increased a mean of 10.8 (SD: 10.7) absolute points from baseline. A weighted analysis of these two populations showed the pooled total UMSARS score at 12-months in patients with MSA in large studies performed in the U.S. had increased a mean of 8.6 (SD: 9.2) points from baseline.

Also, recent studies (38) have determined that the minimally clinically important difference (MCID) in the total UMSARS score is 3.5 points after 48-weeks from baseline.

Taking into consideration this MCID, for this trial, we will assume a promising difference in the UMSARS total score of 4 points between those taking active agent and the historical controls. Specifically, our null hypothesis is that patients receiving sirolimus will have a UMSARS total score progression of only 4.6 points at week 48 higher than baseline, compared to a progression of 8.6 points at week 48 from baseline reported in historical controls from natural history studies and placebo-controlled trials of MSA. Our alternate hypothesis is that sirolimus will be futile to slow the progression of the disease in patients with MSA. The statistical definitions are as follows:

$H_0: \theta_E - \theta_p \leq 4$ where $\theta_p = 8.6$ points increase at week 48 from baseline described in historical controls

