9.4.3 ANALYSIS OF THE SECONDARY ENDPOINT

In order to maintain the overall type I error at the 0.05 level, an hierarchy will be employed as follows: If the primary endpoint is found to be significant at a significance level of 0.05, then the first key secondary endpoint will be tested; if this endpoint is found to be significant in a significance level of 0.05, then the second key secondary endpoint will be tested and so on. The key secondary endpoints and their order in the hierarchy are:

UMSARS sub-scores: The secondary outcome endpoint (UMSARS-1 and UMSARS-2 scores) will be analyzed by comparing the mean decline in total UMSARS-1 and UMSARS-2 score in the active sirolimus group (UMSARS-1 and UMSARS-2 at week 48 minus UMSARS-1 and UMSARS-2 at baseline) with the pre-specified fixed value of 4.5 (SD: 5.5) in each score using a one-sample t-test.

Brain magnetic resonance imaging: The secondary outcome endpoint (putaminal diffusivity) will be analyzed by comparing the mean increase in Trace(D) score in the active sirolimus group (Trace(D) score at week 48 minus Trace(D) score at baseline) with the pre-specified fixed value of 0.07 ($\times 10^{-3}$ mm²/sec) using a one-sample t-test.

Retinal optical coherence tomography: The secondary outcome endpoint (retinal nerve fiber layer

thickness) will be analyzed by comparing the mean decline in RNFL thickness in the active sirolimus group (RNFL at baseline minus RNFL at week 48) with the pre-specified fixed value of 3.7 μm using a one-sample t-test.

Concentration of exosomal αSyn particles: This exploratory outcome endpoint will be analyzed by comparing the mean change in αSyn exosomal particles concentration (week 48 minus baseline) in the active sirolimus group with the placebo group.

In all cases missing data will be addressed by using a regression-based multiple imputation model (78)

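### The exosome hypotheses make the expected reduction the null with no margin, so the test as written cannot support a reduction, and the stated comparator (baseline) conflicts with the planned analysis (placebo)

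*Combined protocol and SAP*

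**What the plan says.** Section 9.1 first states the scientific expectation that sirolimus will lower exosomal alpha-synuclein. It then says that "our null hypothesis is that patients receiving sirolimus will have statistically lower concentration of exosomal" alpha-synuclein "particles at week 48 compared to baseline", and writes the null as "H_0: \theta_E < \theta_p", with the alternative that theta_E is at or above theta_p. Neither symbol is defined for this endpoint. For the UMSARS total score, MRI and OCT, the same section defines theta_p as a value taken from published studies.

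Two other places name a different comparator. The endpoint table in section 3 gives "Change from baseline to week-48 in exosomal alpha-synuclein particle concentration in plasma in patients taking sirolimus versus the placebo group". Section 9.4.3 compares the mean change in alpha-synuclein exosomal "particles concentration (week 48 minus baseline) in the active sirolimus group with the placebo group".

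The status of the endpoint is also mixed. The synopsis, section 3, section 8.1 and the exosome paragraph of 9.4.3 call it exploratory. Section 9.1 places its hypothesis under the secondary efficacy endpoints, and 9.4.3 lists it among the items that follow the testing hierarchy. No alpha, sidedness, named test or decision rule is given for it anywhere.

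**The concern.** Making benefit the null is the convention of this futility trial. It works when a margin separates a promising effect from no effect, because a drug that does nothing then lies well inside the alternative and is likely to be rejected. The exosome hypothesis has no margin, so no effect lies exactly on the boundary, where a level-alpha test rejects with probability alpha only. The sponsor's aim here is also to show a reduction, and a test with the reduction as its null cannot do that.

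The comparator matters separately. A change from baseline within the sirolimus arm is open to drift over 48 weeks and to regression to the mean. A difference in change between randomised arms is not. These are different quantities and can give different answers.

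What is at stake is the reading of one exploratory result. It is nevertheless the only biomarker analysis that uses the placebo arm, since MRI and OCT are tested against fixed published values, and section 4.1 presents it as a marker of autophagy, the drug's proposed mechanism.

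**Working it through.** The plan gives no sample size, power, SD or effect size for exosomes, so there is no figure of its own to reproduce. The check has three parts.

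**1. Margins in section 9.1**

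| Endpoint | Reference value | Null boundary | Margin |
|---|---|---|---|
| UMSARS total | 8.6 | 4.6 | 8.6 − 4.6 = 4 points |
| Putaminal diffusivity (×10⁻³ mm²/sec) | 0.07 | 0.03 | 0.07 − 0.03 = 0.04 |
| RNFL thinning (µm) | 3.7 | 1.45 | 3.7 − 1.45 = 2.25 |
| Exosomal alpha-synuclein | not given | theta_E = theta_p | 0 |

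Section 9.2 gives the origin of the first margin: "we will assume a promising difference in the UMSARS total score of 4 points between those taking active agent and the historical controls".

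**2. How often a drug with no effect keeps the benefit null**

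*Exosomes.* At theta_E = theta_p, P(do not reject) = 1 − alpha, whatever the SD or sample size. The alpha is assumed:
- one-sided 0.05 (the primary endpoint's value, section 9.2): 1 − 0.05 = 95%. Simulating a pooled two-sample t-test 100,000 times gave 94.95% at 42 v 14 and 95.1% at 38 v 13. The second pair is the allocation after about 10% dropout: 42 × 0.9 = 37.8 and 14 × 0.9 = 12.6;
- one-sided 0.025: 97.5%;
- one-sided 0.10: 90%.

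*Primary endpoint, for contrast.* Inputs from section 9.2: margin 4, SD 9.2, one-sided 0.05, n = 38 evaluable or 42 enrolled. For a one-sample t-test the noncentrality is (margin/SD) × √n.
- n = 38: 4/9.2 × √38 = 2.68, power 0.838, benefit null kept 1 − 0.838 = 16%.
- n = 42: 4/9.2 × √42 = 2.82, power 0.870, benefit null kept 13%.

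The plan's own target power of 0.8 corresponds to 20%. So the primary test rejects an inert drug most of the time, while the exosome test rejects it 5% of the time.

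**3. What theta_p could mean**

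- *Placebo arm:* the formula agrees with sections 3 and 9.4.3, and the sentence above it in 9.1 is wrong.
- *Baseline:* the formula agrees with its own sentence and conflicts with sections 3 and 9.4.3. The 95% is then exact only if untreated concentrations do not drift over 48 weeks.
- *Published value, as elsewhere in 9.1:* no such value is given, and the formula agrees with none of the three places.

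Under every reading at least one passage must change.

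**The case against.** The strongest reply is that this is a slip in labelling on an endpoint that decides nothing. Exosomes do not enter the sample size, the go/no-go rule or the interim criteria. Section 9.1 opens by expecting a reduction and speaks of a statistically lower concentration, which is superiority language, so swapped labels are a plausible reading. Placebo is named explicitly in two places, so the intended comparator can be recovered.

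Much of that stands, and it limits what can be concluded. A reader might infer three stronger things that the documents do not support:

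- *That the trial could never show a reduction.* Section 9.4.3 asks only for a comparison of mean change "in the active sirolimus group with the placebo group". An ordinary two-sample analysis would satisfy that and could show a reduction. The limitation belongs to the hypotheses written in 9.1.
- *That an inert drug will be declared beneficial 95% of the time.* The rule that non-rejection is favourable is written for the UMSARS total score only (section 4.1). One-sided 0.05 is also stated for the primary endpoint only, and its justification concerns clinical progression, not a blood marker.
- *That the symbols contradict the sentence because theta_p means placebo.* theta_p is undefined here, and elsewhere in 9.1 it is a published value.

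The futility convention does not answer the point, since the UMSARS total, MRI and OCT hypotheses each carry a margin and this one does not. Nor does a recoverable intention make 9.1 correct: anyone who follows it literally tests the wrong hypothesis.

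**Conclusion.** The hypotheses in section 9.1 are the wrong way round for the stated aim and have no margin. As written, the test can reject a reduction but cannot support one. The sentence that introduces them also uses a comparator different from sections 3 and 9.4.3, and theta_p is undefined. These points follow from the text and need no assumption.

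The size is conditional. It assumes that alpha is one-sided 0.05 and that the primary decision rule is carried over, neither of which the plan states for exosomes. A drug with no effect would then keep the benefit null 95% of the time (90% to 97.5% over one-sided 0.10 to 0.025), against about 16% for the primary endpoint at n = 38. The correction should be made, but it is a matter of wording on an exploratory endpoint. The primary conclusion and the sample size do not depend on it.

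**What to change.** In section 9.1:

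- Define theta_E and theta_p as the mean change in exosomal alpha-synuclein concentration from baseline to week 48 in the sirolimus and placebo arms.
- Set H0: theta_E − theta_p ≥ 0 and H1: theta_E − theta_p < 0.
- Replace the comparison with baseline by the comparison with placebo, to agree with sections 3 and 9.4.3.
- Move the endpoint out of the secondary list and label it exploratory.

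In section 9.4.3:

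- Name the test and state the alpha.
- Report the between-arm difference with a matching confidence interval: 90% for one-sided 0.05, or 95% for one-sided 0.025.
- State that the endpoint is outside the secondary hierarchy.

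Keeping benefit as the null and adding a justified margin would also separate benefit from no effect. However, the plan gives no effect size or SD from which to set a margin, and reversal fits the stated aim better.

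After reversal, a drug with no effect would be called beneficial 5% of the time at one-sided 0.05 (simulated 5.0%). Precision is modest: the reduction detectable with 80% power is 0.78 SD at 42 v 14 and 0.81 SD at 38 v 13 (0.88 and 0.92 SD at one-sided 0.025), so the interval should lead the report. The cost is a few lines of wording, with no added patients, visits or assays.
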